7.4. Subject Disposition

Study completion and reasons for discontinuation for all randomized subjects in the double-blind phase will be summarized for each treatment group by simple tabulation. Discontinuations by reason will be tabulated by visit for each treatment group.

CONFIDENTIAL

This material is the property of Vanda Pharmaceuticals Inc. Do not disclose or use except as authorized in writing by the study sponsor.

7.5. Demography and Other Baseline Data

The data documented in this trial and the parameters measured at screening/baseline will be summarized using classic descriptive statistics: mean, median, SD, CV%, minimum and maximum values (for quantitative variables) and by frequencies (qualitative variables). Data not available will be assessed as “missing values”. Past and current medical history will be summarized by treatment group using the system organ class (SOC) as coded using the Medical Dictionary for Regulatory Activities (MedDRA) coding dictionary.

7.6. Prior/Concomitant Therapy

Any medications or therapy present before the first dose of study medication (Visit 2) will be considered as prior medications. Concomitant medications (medications present while on study medication) will be recorded throughout the study and at early discontinuation. These medications will be coded using the WHO-drug dictionary. The number of subjects from the Safety Set using prior or concomitant medications will be categorized by the WHO-drug category and preferred term, and presented for each treatment group. In any given category (e.g., drug category) a subject will be counted only once.

7.7. Outcomes

7.7.1. Primary outcome (including definition)

One primary outcome will be considered in this study:

- TST_{2/3} which is defined as the total sleep time during the first 2/3 of night following an 8-hour phase advance bedtime, as measured by polysomnography.

The primary null hypothesis is that there is no difference in TST_{2/3} between subjects receiving tasimelteon and subjects receiving placebo. TST_{2/3} will be assessed by analysis of variance with treatment group, and clinical site as a main effect. The primary efficacy analysis will be based on the ITT population.

Details on the complete analysis can be found in the Statistical Analysis Plan.

CONFIDENTIAL

This material is the property of Vanda Pharmaceuticals Inc. Do not disclose or use except as authorized in writing by the study sponsor.

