VP-VEC-162-3107
Confidential

Vanda Pharmaceuticals
February 23, 2018

The JET8 study: a double-blind, placebo-controlled study to investigate tasimelteon in healthy subjects with jet lag type insomnia induced by an 8-hour phase advance

Authors:

Document type:

Clinical Study Protocol

Sponsor:

Vanda Pharmaceuticals Inc.
[name]
[name]
[name]

Study Product:

Tasimelteon

Protocol Number:

VP-VEC-162-3107

Study Phase

III

IND Number:

128352

Date: February 23, 2018

Version number Amendment 4

Number of Pages 65

CONFIDENTIAL

This document is confidential and the property of Vanda Pharmaceuticals Inc. No part of it may be transmitted, reproduced, published, or used by other persons without prior written authorization from the study sponsor.

Name of Sponsor/Company: Vanda Pharmaceuticals Inc.	
Name of Investigational Product: Tasimelton/VEC-162	
Name of Active Ingredient: Tasimelton/VEC-162	
Title of Study: The JET8 study: a double-blind, placebo-controlled study to investigate tasimelton in healthy subjects with jet-lag type insomnia induced by an 8-hour phase advance.	
Study center(s): Multicenter (USA)	
Studied period: Estimated date first subject enrolled: October 2017 Estimated last subject enrolled: December 2017	Phase of development: Phase III
Number of subjects (planned): Up to 300 eligible subjects will be randomized and assigned to 20 mg tasimelton or placebo in a 1:1 ratio. Treatment assignments will be made according to a randomization schedule.	
Diagnosis and main criteria for inclusion/exclusion: Healthy males or females 18-75 years of age, inclusive, who meet inclusion criteria.	
Investigational product, dosage and mode of administration: Tasimelton will be administered orally as a dose of 20 mg. Tasimelton dosage form will be size 1, dark blue, opaque, hard gelatin capsules with two white bars on the capsule body and cap, and filled with white to off-white powder.	
Duration of treatment: 1 day/1 night	
Reference therapy, dosage and mode of administration: Placebo capsules will be provided in size and appearance identical to those containing tasimelton and will be administered orally	

CONFIDENTIAL

This material is the property of Vanda Pharmaceuticals Inc. Do not disclose or use except as authorized in writing by the study sponsor.

Objectives:**Primary Objectives:**

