This study will be divided into 2 phases: the screening phase and the randomization/evaluation phase. The screening phase consists of the screening visit, during which inclusion/exclusion criteria will be assessed and the baseline evaluations will be conducted. The randomization phase consists of a 1-day/1-night double-blind evaluation period in which the subject's bedtime is advanced 8 hours. The screening visit and day/night in sleep clinic will be separated by at least 1 week. Subjects meeting all entry criteria for the study will enter the randomization phase. Eligible subjects will be admitted to a sleep clinic for one day and night of evaluation. Bedtime will be determined by their habitual bedtime (as determined from screening) in the originating time zone. For example, if a subject has a habitual bedtime of 22:00 they will be put to bed at 14:00, or 22:00 in the new "time zone." A PSG will be performed throughout the night beginning prior to bedtime in the "new time zone." Following the 8-hour phase advanced sleep, subjects will complete post-sleep questionnaire, KSS and VAS assessments. During this time subjects will also be provided with breakfast and lunch. After completing all required study procedures, the subjects be discharged from the study clinic. Throughout the study the subject's sleep pattern will be monitored with an actiwatch and through subject reported sleep diaries.

[figure not shown]
[figure not shown]
Statistical Methods:

Nighttime sleep will be assessed by analysis of variance, with treatment group, clinical site, as main effect. A comparison will be made between the subjects treated with tasimelteon 20 mg and placebo. The primary efficacy analysis will be based on the ITT population.

The statistical analyses will be detailed in the Statistical Analysis Plan.

CONFIDENTIAL

This material is the property of Vanda Pharmaceuticals Inc. Do not disclose or use except as authorized in writing by the study sponsor.

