7. STATISTICAL PLAN

This section describes the planned statistical analyses in general terms. A complete description of the methodology will be specified in a statistical analysis plan (SAP), which will be finalized prior to unblinding. Any changes in the statistical methods described in this protocol that occur prior to unblinding will be documented in the statistical analysis plan and will not require a protocol amendment.

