7.1. General Statistical Design

The study is a multi-center, two-arm, placebo-controlled parallel group pivotal study of the effect of tasimelteon in healthy subjects with jet lag type insomnia. Subjects will be randomized to receive either an active dose of tasimelteon 20 mg or placebo. The primary aim of the study is to ascertain whether tasimelteon is superior to placebo for the reduction of jet lag type insomnia. This study will investigate the effect of treatment on “first-night” jet lag type insomnia by measuring sleep objectively through PSG and the next-day residual effects of treatment. The primary outcome measure is total sleep time (TST) during the first 2/3 of the night (denoted by $TST_{2/3}$) following 8-hour phase advance bedtime, other

CONFIDENTIAL

This material is the property of Vanda Pharmaceuticals Inc. Do not disclose or use except as authorized in writing by the study sponsor.

objective measures (TST in other time intervals, SE, LPS, WASO, Total REM sleep time, total Non-REM sleep time, Latency to REM, and time to accumulate 30 minutes of REM sleep) and subjective next-day effects (KSS and VAS) being secondary outcomes that will provide supportive evidence. The safety and tolerability of tasimelteon will also be explored.

The randomization will be in a 1:1 ratio between the 20mg and placebo groups, and will be stratified by investigative site. The length of follow-up (a screening stage plus day into overnight assessment stage) was chosen in order to assess the “first-night effect” of tasimelteon in healthy volunteers.

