7.2. Sample Size and Accrual

The standard deviation is based on data from the tasimelteon Study VP-VEC-162-3101 comparing doses of VEC-162 and placebo in healthy volunteers in a 5 hour phase advance model. To detect a 30 minute difference in TST_{2/3} between tasimelteon-treated subjects versus placebo with a standard deviation (SD) of 75, a sample size of 150 subjects per arm provides approximately 93% power with a two-sided alpha=0.05. This sample size also provides at least 85% power to detect the difference of 28 mins (SD 80) in TST between tasimelteon treated vs. placebo group.

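### Optional gain in precision: the primary TST2/3 model is valid but uses no subject-level covariate, although age is known for every subject

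*Combined protocol and SAP*

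**What the plan says.** Section 7.7.1 gives the primary analysis: "TST_{2/3} will be assessed by analysis of variance with treatment group, and clinical site as a main effect". The synopsis, under Statistical Methods, gives the same model: "Nighttime sleep will be assessed by analysis of variance, with treatment group, clinical site, as main effect". Neither place names a subject-level covariate. Section 7.1 says that randomisation "will be stratified by investigative site", so the one stratification factor is in the model.

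The synopsis sets the entry range: "Healthy males or females 18-75 years of age, inclusive, who meet inclusion criteria". In the analysis text, age appears only in section 7.9, as one possible subgroup factor. Section 7.7.2 provides for analysis of covariance on secondary variables where the endpoint has its own baseline. PSG is described only for the in-clinic night, so TST2/3 has no such baseline.

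Sections 7 and 7.7.1 leave the full method to the SAP. The text available contains the protocol's statistical section and no separate detailed SAP. Section 7 adds that changes to the methods made before unblinding "will be documented in the statistical analysis plan and will not require a protocol amendment".

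**The concern.** Nothing in the stated model is invalid, and leaving out a covariate fits the rule in section 7.7.2. The question is one of efficiency. With no baseline PSG, the usual covariate for a sleep endpoint is not available, so any gain has to come from another pre-treatment variable. Age is the easiest candidate: the entry range is wide, the value is fixed before treatment, and it needs no derivation or imputation.

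If age explains part of the between-subject variation in TST2/3, a treatment and site model leaves that part in the residual. Chance imbalance in age between arms is then ordinary sampling error, which alpha and the confidence interval already cover. What is at stake is a somewhat wider interval and slightly lower power on the single primary test, in a trial already planned at about 93%.

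**Working it through.** **Inputs.** From section 7.2: difference 30 min, SD 75, 150 per arm, two-sided alpha 0.05, stated power about 93%. For full-night TST: "This sample size also provides at least 85% power to detect the difference of 28 mins (SD 80) in TST". On the origin of the SD, section 7.2 says: "The standard deviation is based on data from the tasimelteon Study VP-VEC-162-3101". It does not say whether the SD is raw or residual; here it is taken as unadjusted. The R² of age, beyond site, is not in the documents, so 0, 1, 5 and 10% are assumed.

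**Step 1: reproduce the plan's figures.**
- TST2/3: SE = 75 × √(2/150) = 8.660 min; noncentrality = 30/8.660 = 3.464; df = 298; critical t = 1.968. Power is 93.23% by the noncentral t, which agrees with the stated figure. The 95% CI half-width is 1.968 × 8.660 = 17.04 min.
- Full-night TST: SE = 80 × √(2/150) = 9.238 min; noncentrality = 28/9.238 = 3.031. Power is 85.57%, which agrees with the stated minimum of 85%. The half-width is 18.18 min.

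**Step 2: add age.** The variance entering the treatment comparison becomes SD² × (1 − R²) × (1 + 1/296), with df = 297. The factor 1 + 1/296 is the price of estimating one covariate. The equivalent sample size per arm under the current model is 150 / [(1 − R²)(1 + 1/296)].

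Worked line for R² = 5%: effective SD = 75 × √(0.95 × 1.00338) = 73.22; SE = 8.455 min; noncentrality = 30/8.455 = 3.548; power = 94.26%; half-width = 1.968 × 8.455 = 16.64 min.

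| Model | TST2/3 power | Half-width (min) | Equivalent n/arm | Full-night TST power | Half-width (min) |
|---|---|---|---|---|---|
| Treatment + site (now) | 93.23% | 17.04 | 150 | 85.57% | 18.18 |
| + age, R² = 0 | 93.15% | 17.07 | 149.5 | 85.46% | 18.21 |
| + age, R² = 1% | 93.38% | 16.99 | 151.0 | 85.80% | 18.12 |
| + age, R² = 5% | 94.26% | 16.64 | 157.4 | 87.17% | 17.75 |
| + age, R² = 10% | 95.29% | 16.20 | 166.1 | 88.87% | 17.28 |

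**Step 3: thresholds for TST2/3.** If age is useless, the loss is 93.23 − 93.15 = 0.08 percentage points and 17.07 − 17.04 = 0.03 min. Power breaks even at R² = 0.34% (correlation √0.0034, about 0.06). A gain of one full point needs R² = 4.87% (correlation √0.0487, about 0.22).

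**Step 4: robustness.** Charging degrees of freedom for 5, 10 or 20 sites (number assumed) changes power by at most 0.02 points and puts break-even at 0.34 to 0.36%. A simulation used 20,000 trials per scenario, with 10 sites, 1:1 allocation within site, age uniform on 18 to 75 and a linear age effect (all assumed). At R² of 0, 1, 5 and 10%, the age model had type I error of 4.90, 4.80, 5.04 and 4.90% (Monte Carlo SE about 0.15) and power of 93.0, 93.0, 94.2 and 95.3%.

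**Step 5: a smaller true effect.** If the difference were 25 min (an assumption), current power would be 82.1%, rising to 83.8% at R² = 5% and 85.7% at 10%.

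**The case against.** The strongest reply is that there is no defect to correct. The model matches the randomisation, the covariate rule in section 7.7.2 is followed, and declining to add a prognostic covariate is a legitimate choice. This is true, and the point is not put as an error.

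The benefit also rests on something the documents do not supply. Nothing in them says that age predicts TST2/3 after an 8-hour advance, or that age would do better than gender, which section 7.9 also lists. At R² = 1% the gain is 0.15 points, and the simulation shows no visible difference. If SD 75 is already a residual SD, the gain over the stated power is smaller. All of this stands, and it is why the result is given as a range that includes a small loss.

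The SAP may already name covariates. Section 7 describes the analyses only in general terms, so this cannot be excluded.

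Timing is the most practical objection. This version is dated February 23, 2018, and the synopsis has "Estimated last subject enrolled: December 2017". If enrolment kept to that estimate, the primary model of a pivotal trial would change after data collection. That is acceptable only while the study is blinded.

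These arguments limit the weight of the point. They do not remove it, because the downside is known and very small while the possible gain is larger.

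**Conclusion.** The point holds as an optional, low-cost improvement. The stated analysis is valid and may stand. Across assumed R² values of 0 to 10%, adding age changes power for TST2/3 by between −0.08 and +2.1 points (95.29 − 93.23 = 2.06). It changes the CI half-width by between +0.03 and −0.85 min (16.20 against 17.04 in the table; 0.85 before rounding). At R² of 5 to 10% that equals about 7 to 16 more subjects per arm without further recruitment.

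This rests on four assumptions: SD 75 is unadjusted; the R² range is plausible; age is recorded for every subject, which is inferred from the entry criterion; and the study is still blinded. Confidence is medium, because the size of the gain cannot be settled from the documents.

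**What to change.** Optional, and only before unblinding:

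- State in the SAP that TST2/3 is analysed by ANCOVA with treatment, site and age, with age continuous and linear.
- Use the same model for full-night TST. This largely follows already from section 7.7.2, which has continuous secondary variables analysed like the primary.
- Keep the treatment and site ANOVA as a sensitivity analysis.
- Keep actigraphy-derived sleep out of the primary model. Unlike age, it would need rules for derivation and missing data.

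If the SAP already names covariates, only check that it agrees with the synopsis and section 7.7.1. If the data are unblinded, leave the primary model as stated.

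The cost is one sentence in the SAP, one extra sensitivity analysis and one of 298 degrees of freedom. No new data are needed. Section 7 allows the change without a protocol amendment, but the SAP should record that it departs from the model in the synopsis and section 7.7.1.

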7.7.2. Secondary outcomes

The secondary outcomes of the study are as follows:

- WASO, as measured by polysomnography. WASO is defined as the time spent awake in the period between onset of persistent sleep and lights on.
- LPS by PSG which is defined as the length of time elapsed between light-out and onset of persistent sleep. Persistent sleep is defined as the point at which 10 minutes of non-wake sleep has begun.
- The full night (as well as parts of the night) SE, defined as the total sleep time (measured by polysomnography) as a percentage of the total time spent in bed between lights off and lights on and full night TST.
- TST in other time intervals of the night, e.g. TST_{3/4} as the total sleep time during the first ¾ of the night (i.e. first 6 hours).
- Total REM sleep time, total Non-REM sleep time, Latency to REM, time to accumulate 30 minutes of REM sleep.
- The subjective post sleep assessments of sleep quality, sleep latency, and total sleep time as collected via post-sleep questionnaire.
- The next day residual effects of tasimelteon:
KSS, VAS and post-sleep questionnaire (PSQ)
- The safety and tolerability of 20 mg tasimelteon.

For the continuous secondary efficacy variables, descriptive statistics will be presented by treatment group, and the scores will be summarized and analyzed in a manner similar to that for the primary endpoint. When baseline is available for endpoint, analysis of covariance will be used by including baseline as a covariance. Categorical variables will also be summarized and evaluated. Details of the analysis will be described in the SAP.

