1. To assess the effects of tasimelteon 20 mg on nighttime sleep parameters as measured by Polysomnography (PSG) after an 8-hour phase advanced bedtime representative of transmeridian travel across 8 time zones.

Secondary Objectives:

1. To assess the effects of tasimelteon 20 mg on nighttime objective sleep parameters.
2. To assess the effects of tasimelteon 20 mg on nighttime and daytime subjective parameters.
3. To assess the safety and tolerability of single oral doses of tasimelteon 20 mg.

Overall Design:

This is a multicenter, randomized, double-blind, placebo-controlled, parallel pivotal trial to investigate the efficacy and safety of a single 20 mg oral dose of tasimelteon and matching placebo in healthy male and female subjects with jet lag type insomnia from an 8-hour phase advance.

Screening**V1**

IE
KSS
VAS

Evaluation**V2**

KSS KSS
VAS VAS

1 week

In-patient segment
1 day/1 night

Actigraphy and Sleep Diaries

PSG

Tasi or PBO

Pre-Sleep (baseline KSS & VAS)

Post-Sleep (KSS & VAS: 90 minutes after wake then once every 2 hrs)

EOS

CONFIDENTIAL

This material is the property of Vanda Pharmaceuticals Inc. Do not disclose or use except as authorized in writing by the study sponsor.

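### Is the standing of full-night TST left unclear by the broad synopsis objective, its own power figure and an open secondary list?

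*Combined protocol and SAP*

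**What the plan says.** The synopsis primary objective is broad: "To assess the effects of tasimelteon 20 mg on nighttime sleep parameters as measured by Polysomnography (PSG) after an 8-hour phase advanced bedtime". Secondary objective 1 covers much the same ground: "To assess the effects of tasimelteon 20 mg on nighttime objective sleep parameters". The synopsis statistical paragraph is equally general: "Nighttime sleep will be assessed by analysis of variance, with treatment group, clinical site, as main effect". The synopsis text available (its figures are not shown) does not name TST2/3.

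Section 7 is specific. Section 7.1 names TST2/3 as the primary outcome measure. It lists the other objective measures, including TST in other time intervals, as "being secondary outcomes that will provide supportive evidence". Section 7.7.1 opens with "One primary outcome will be considered in this study" and gives the null hypothesis for TST2/3. Section 7.7.2 names full-night TST at the end of the sleep-efficiency (SE) item, in an unranked list. It leaves the windows open for SE ("The full night (as well as parts of the night) SE, defined as the total sleep time") and for TST ("TST in other time intervals of the night, e.g").

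Section 7.2 sizes the trial on TST2/3 and then adds: "This sample size also provides at least 85% power to detect the difference of 28 mins (SD 80) in TST". It states no window for that second TST.

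Section 7 says that the full methodology will be in a SAP finalised before unblinding, and Sections 7.7.1 and 7.7.2 refer analysis details to it. The text of that SAP is not among the pages reviewed.

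**The concern.** Only two endpoints in the plan have a power statement, TST2/3 and TST. A separate power statement often marks a key secondary endpoint that is meant to carry a claim. Here the second endpoint also falls under the wording of the primary objective, and Section 7.7.2 neither ranks it nor gives a testing order. A reader could therefore ask whether full-night TST is a confirmatory second test or only supportive.

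Two things would be at stake. If the two endpoints disagreed, the broad objective might be called met on full-night TST when TST2/3 had failed, and the error rate for that objective would exceed 5%. If windows were chosen after unblinding, a favourable one could be picked.

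**Working it through.** **1. The plan's own power figures.** Inputs from Section 7.2: 150 per arm; two-sided alpha 0.05 (stated for TST2/3, assumed to carry over to TST); difference 30 min with SD 75 for TST2/3; difference 28 min with SD 80 for TST. With the normal approximation, power = Φ(δ / (SD × √(2/n)) − 1.960), and √(2/150) = 0.11547.

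- TST2/3: 30 / (75 × 0.11547) = 3.464; Φ(3.464 − 1.960) = 93.4%. Stated: approximately 93%.
- TST: 28 / (80 × 0.11547) = 3.031; Φ(3.031 − 1.960) = 85.8%. Stated: at least 85%.

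The noncentral t on 298 degrees of freedom gives 93.2% and 85.6%. Both statements are correct.

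**2. What each section says about full-night TST.**

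| Place | Standing given |
|---|---|
| Synopsis, primary objective | No endpoint named; covers every PSG measure |
| Synopsis, secondary objective 1 | Covers TST too, with the other objective measures |
| Section 7.1 | TST outside the first two thirds is secondary and supportive |
| Section 7.2 | A power figure that the chosen sample size also provides; no role assigned |
| Section 7.7.1 | Not primary; the single primary outcome is TST2/3 |
| Section 7.7.2 | Listed among the secondary outcomes |

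The whole night is an interval other than the first two thirds, so Section 7.1 covers it. The three sections that assign a role agree. The synopsis objective gives TST no special place, because the same words cover wake after sleep onset, latency to persistent sleep and the rest.

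**3. How far the two endpoints could diverge.** Section 7.7.2 equates three quarters of the night with 6 hours, so the night is 480 min and the last third is 160 min. Sleep time in that third lies between 0 and 160 min, so its SD, s, is at most 80. Full-night TST is TST2/3 plus that part, hence

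- covariance of the two parts = (80² − 75² − s²) / 2
- correlation of TST2/3 with TST, r = (75² + covariance) / (75 × 80)

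Two cases:

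- s = 80, the extreme: covariance = (6400 − 5625 − 6400) / 2 = −2812.5; r = 2812.5 / 6000 = 0.47. Half the subjects would sleep none of the last third and half would sleep all of it.
- Parts uncorrelated: s = √775 = 27.8; r = 5625 / 6000 = 0.94.

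At the design effects (bivariate normal):

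| r | Both significant | TST2/3 only | TST only |
|---|---|---|---|
| 0.47 | 82.0% | 11.4% | 3.8% |
| 0.94 | 85.5% | 7.9% | 0.3% |
| 1.0 | 85.8% | 7.6% | 0% |

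The troublesome pattern, TST significant without TST2/3, occurs in at most 3.8% of trials. In that case Section 7.7.1 decides: the primary outcome has not been met.

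**4. The error rate under a rule the plan does not have.** If either endpoint at 0.05 counted as success and both were null, the error would be 9.2% at r = 0.47, 6.6% at r = 0.94 and 5.0% at r = 1. Under the plan as written it is 5%, on TST2/3 alone.

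**5. All named secondaries together.** Section 7.7.2 names 14 efficacy measures. If all were independent, null and tested at 0.05, the chance of at least one p < 0.05 would be 1 − 0.95¹⁴ = 51%. That case cannot arise. On a fixed 480-min night, full-night SE is TST / 480, so one test is counted twice, and REM plus non-REM time make up TST. Nor does the plan rest its primary conclusion on any of these.

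**The case for a change.** The best case for a change is that Section 7.1 applies the supportive label to every secondary alike, and so does not explain why one of them was given a power figure. In a pivotal trial it would be cheap to state a rank, and a list of windows fixed in advance answers any suspicion of selection, which cannot be dispelled afterwards. The overlap of the two objectives sits in the synopsis itself, and a SAP would not alter it.

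Parts of this stand. The objectives do overlap, Section 7.2 does not name the window for its second figure, and Section 7.7.2 leaves TST and SE windows open with no testing order. But an objective states an aim, and Sections 7.1 and 7.7.1 turn it into a test. A power figure for a secondary outcome shows that the sample is adequate for it and confers no confirmatory role. Windows and any ordering are the kind of detail that Section 7 assigns to the SAP, with a deadline before unblinding. As that SAP was not available to this review, it cannot be said that the detail is missing.

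**Conclusion.** The concern does not hold as a reason to change the plan. Full-night TST is a supportive secondary outcome by Sections 7.1, 7.7.1 and 7.7.2, and its power figure is correct. The primary test of TST2/3, its two-sided 5% level and 150 per arm are sound as written. The figures of 9.2% and 51% depend on an either-endpoint success rule and on 14 independent nulls respectively, and the plan contains neither.

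What is left is drafting: overlapping synopsis objectives, an unnamed window in Section 7.2, and windows given by example in Section 7.7.2. An analyst following Section 7 would read TST in 7.2 as full-night, take the windows from the SAP and treat secondary p-values as supportive.

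This rests on three assumptions: the SAP is finalised before unblinding, as Section 7 requires; it fixes the windows; and no formal claim on a secondary outcome is made outside it.

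### Does the plan lose subjects who never reach persistent sleep, REM or 30 minutes of REM from the latency analyses?

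*Combined protocol and SAP*

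**What the plan says.** Section 7.7.2 gives the secondary sleep outcomes. One is "LPS by PSG which is defined as the length of time elapsed between light-out and onset of persistent sleep". Three REM-based outcomes and one non-REM outcome are listed by name only: "Total REM sleep time, total Non-REM sleep time, Latency to REM, time to accumulate 30 minutes of REM sleep". For continuous secondary efficacy variables, "the scores will be summarized and analyzed in a manner similar to that for the primary endpoint"; section 7.7.1 sets the primary analysis as ANOVA with treatment group and clinical site, in the ITT population. The same section closes with "Details of the analysis will be described in the SAP".

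Three other places bear on the point:

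- Section 7.3 admits to ITT every randomised, dosed subject with PSG data. Reaching sleep or REM is not a condition.
- The opening of section 7 says that it covers the analyses in general terms, that the full methodology goes into a SAP finalised before unblinding, and that changes of method before then need no protocol amendment.
- Section 7.5 has the only sentence on unavailable data, "Data not available will be assessed as" missing values. It sits among the screening and baseline summaries.

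The text available is the synopsis and section 7 of the protocol. It contains no separate SAP text.

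**The concern.** Each of the three latencies is the time to an event that may not happen before lights-on. Bedtime is moved 8 hours earlier to induce insomnia, and 30 minutes of REM has to be accumulated, not merely begun, so non-attainment is plausible. A subject without the event is in ITT but has no number, and ANOVA needs one for each subject. A program run on blanks would leave those subjects out.

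The comparison would then rest on a subset selected by an outcome after randomisation, with the worst results removed. If the drug makes the event more likely, more subjects are lost from placebo and a real benefit is understated.

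WASO has a related gap. The plan says "WASO is defined as the time spent awake in the period between onset of persistent sleep and lights on", so WASO is undefined without onset, and a score of 0 would give such a subject the best possible result.

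**Working it through.** **1. The plan's own figures.** Section 7.2 gives 150 per arm and two-sided alpha 0.05.

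- TST_2/3, difference 30 min, SD 75: z = 30 / (75 × √(2/150)) = 30 / 8.66 = 3.46. Power = Φ(3.46 − 1.96) = 0.934, against about 93% stated.
- Full-night TST, difference 28 min, SD 80: z = 28 / (80 × √(2/150)) = 28 / 9.24 = 3.03. Power = Φ(3.03 − 1.96) = 0.858, against at least 85% stated.

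Both reproduce. TST has a value (possibly zero) for anyone with PSG, so the concern does not touch them.

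**2. The ceiling.** Section 7.7.2 describes the first three quarters "of the night (i.e. first 6 hours"). The night is therefore 6 / 0.75 = 8 hours, or 480 min.

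**3. Is exclusion stated?** No. Section 7.7.2 asks for an analysis similar to the primary one and defers its details. The missing-values wording in section 7.5 concerns screening and baseline data, so it does not govern PSG results after dosing. What the text shows is an unwritten rule.

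**4. Would capping at 480 be a clear gain?** The documents give no non-attainment rate and no distribution of times. Everything below is assumed: 150 per arm, 10 sites, ANOVA on treatment and site.

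*Model A: the drug shortens every time by a fixed factor.* Four shapes: log-normal with SD(log) 0.5, times 15% shorter; log-normal with SD(log) 1.0, 25% shorter; Weibull shape 2, 15% shorter; Weibull shape 1, 25% shorter. There were 20,000 simulated trials per scenario. The gain ranges are over the four shapes and were taken before rounding.

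| Placebo non-attainment | Power (%) if dropped | Power (%) if set to 480 | Gain (points) |
|---|---|---|---|
| 0.1% | – | – | −0.4 to 0.9 |
| 1% | 74.2 / 52.8 / 70.5 / 62.9 | 75.7 / 54.6 / 75.9 / 69.0 | 1.5 to 6.0 |
| 10% | 61.6 / 45.2 / 41.3 / 34.8 | 77.2 / 62.8 / 71.4 / 64.4 | 15.6 to 30.1 |

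With no drug effect, both methods reject in 4.6% to 5.3% of trials. This model ties the non-attainment rate to the median. For a log-normal, the placebo median is 480 × exp(−SD × z). At 1% and SD 0.5 that is 480 × exp(−0.5 × 2.326) = 150 min. The four implied medians are 150 / 47 / 186 / 72 min at 1% and 253 / 133 / 263 / 144 min at 10%. Nothing in the documents supports them for any of the three endpoints. The model also forces non-attainment to fall with the drug.

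*Model B: some subjects never attain, and the drug shortens the times of the rest.* Log-normal times, 2,000 trials per row.

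| Placebo median, SD(log), shortening | Non-attainment, placebo / drug | Power (%) if dropped | Power (%) if set to 480 |
|---|---|---|---|
| 60 min, 0.8, 25% | 1% / 1% | 76 | 61 |
| 60 min, 0.8, 25% | 2% / 2% | 78 | 53 |
| 60 min, 0.8, 25% | 2% / 1.5% | 76 | 64 |
| 60 min, 0.8, 25% | 5% / 3.75% | 76 | 52 |
| 60 min, 0.8, 25% | 10% / 5% | 72 | 80 |
| 30 min, 0.5, 15% | 2% / 2% | 75 | 12 |

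Repeat runs agreed within about 3 points.

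**5. Why the sign turns, by hand (60 min, 2% / 2%).**

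- Placebo mean among attainers: 60 × exp(0.8²/2) = 82.6 min. Drug mean: 0.75 × 82.6 = 62.0 min. Difference: 20.7 min.
- SDs: mean × √(exp(0.64) − 1) = 78.2 and 58.7 min.
- Dropped, 147 per arm: SE = √((78.2² + 58.7²)/147) = 8.07; z = 2.56; power about 73%.
- Set to 480: the difference becomes 0.98 × 20.7 = 20.2 min. Each variance becomes 0.98 × SD² + 0.02 × 0.98 × (480 − mean)², so the SDs rise to 95.4 and 82.5 min. SE = √((95.4² + 82.5²)/150) = 10.3; z = 1.97; power about 50%.

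The difference hardly moves. A few values at 480 min inflate the variance, and the power goes with it. The normal approximation is within about 5 points of the simulation.

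**6. WASO.** Scoring 0 without onset shifts the arm difference by (p0 − p1) × mean WASO, where p0 and p1 are the placebo and drug non-attainment rates. With an assumed mean of 100 min and Model A rates, that is 0.0055 to 0.0083 × 100 = 0.6 to 0.8 min at 1%, and 0.0417 to 0.0587 × 100 = 4 to 6 min at 10%.

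**The case for a change.** The strongest case for a change is that the rule costs one SAP sentence, needs no amendment before unblinding, and keeps the ITT comparison intact. Under Model A the gain is material, and the difference in minutes among attainers falls short of the capped difference by 7% to 12% at 1% non-attainment and 26% to 42% at 10%. Section 7.1 relies on these endpoints as supportive evidence in a pivotal trial.

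Much of this stands. No supplied text gives the rule, and dropping non-attainers would not be an ITT analysis. The argument from principle for keeping everyone is sound.

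The argument from power does not stand as a general one, because Model B reverses it with equally unsupported inputs. The 480-minute rule also needs a time origin that section 7.7.2 does not give for latency to REM. If that latency runs from sleep onset, 480 min exceeds what could be observed. Rank or censored methods are less exposed to a few capped values, but their order also depends on the shape. At 1% in Model A, a site-stratified rank test (van Elteren) has 77.3 / 66.6 / 66.4 / 56.0% power and a stratified log-rank test 71.9 / 60.9 / 76.0 / 65.2%. For WASO, declaring the value undefined still leaves those subjects without one.

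**Conclusion.** No change to the plan follows. This is a gap in a general description, and the protocol itself assigns it to the SAP. An analyst writing that SAP would ordinarily define where latency to REM starts, decide how non-attainers enter each analysis, count them by arm, and avoid scoring WASO as 0 when there was no persistent sleep.

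The stakes are limited. The primary TST_2/3 analysis and its roughly 93% power are unaffected. Type I error stays near 5% with either handling in the Model A simulations. The endpoints concerned are supportive.

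The size of any effect on power is unknown. Over the scenarios shown in the working, capping at 480 min in the ANOVA changes power by anything from a gain of 30.1 points (Model A, 10% placebo non-attainment) to a loss of 63 points (75% − 12%, Model B, 30 min median). That range rests wholly on assumed rates and shapes. The choice between capped means, ranks and censored times is therefore a fair trade-off. The conclusion would differ if the finalised SAP expressly excluded non-attainers, but nothing in the available text says so.
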